7.5. Exclusion Criteria

Subjects will not be eligible to participate in this study if any one of the following exclusion criteria is met:

1. Current diagnosis of Acquired Immune Deficiency Syndrome (AIDS).
2. Current diagnosis of chronic pain requiring opioids for treatment.
3. Current DSM-V diagnosis for moderate to severe substance use disorder (including alcohol) other than opioids, caffeine or nicotine and currently being treated as the primary substance use disorder.
4. Recent history of or current evidence of suicidal ideation or active suicidal behavior as based on the Columbia Suicide Severity Rating Scale (C-SSRS) ("Yes" responses to questions 4 or 5).
5. Pregnant or lactating or planning to become pregnant during the study.
6. Hypersensitivity or allergy to naloxone (only for subjects receiving the SL BPX test dose), BPN or excipients of CAM2038.
7. Requires chronic use of agents that are strong inhibitors or inducers of cytochrome P450 3A4 (CYP 3A4) such as some azole antifungals (e.g., ketoconazole), macrolide antibiotics (e.g., clarithromycin), or protease inhibitors (e.g., ritonavir, indinavir, and saquinavir).
8. Hepatitis, unless under stable treatment, at the discretion of the Investigator.
9. Any pending legal action that could prohibit participation or compliance in the study.
10. Exposure to any investigational drug within the 4 weeks prior to Screening.
11. Aspartate aminotransferase (AST) levels ≥ 3 X the upper limit of normal, alanine aminotransferase (ALT), levels ≥ 3 X the upper limit of normal, total bilirubin ≥ 1.5 X the upper limit of normal, or creatinine ≥ 1.5 X upper limit of normal on the Screening laboratory assessments, or other clinically significant laboratory abnormalities, which in the opinion of the Investigator may prevent the subject from safely participating in study.
12. Participants with a history of risk factors of Torsades de Pointes (e.g., heart failure, hypokalemia, family history of Long QT Syndrome) or an ECG demonstrating a Fridericia's corrected QT interval (QTcF) >450 msec in males and QTcF > 470 in females at screening.

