11.3.3. Analysis of Safety Assessments

Exposure and safety summaries will be presented for both Safety Populations.

All AEs will be coded by primary system organ class (SOC) and preferred term according to the Medical Dictionary for Regulatory Activities (MedDRA), and summarized by number and percent of subjects in each primary SOC and preferred term. Summaries of these AE subsets will

be presented for relationship to study drug, intensity, seriousness, AEs or SAEs leading to discontinuation and AEs occurring in 5% or greater (by preferred term). Frequencies for deaths and hospitalizations will also be summarized.

Data for clinical laboratory tests, ECG, vital signs, and physical and injection site examinations will be summarized using standard descriptive and change from baseline statistics. Shift tables and tabular summaries of abnormalities will be provided, where appropriate. Medications will be coded using the World Health Organization Drug dictionary and summarized using descriptive statistics.

By-subject listings will be provided for all safety data.

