6.0 GENERAL CONVENTIONS

Unless otherwise stated, all analyses will be performed using SAS Version 9 and all hypothesis tests will be conducted at a two-sided significance level of 0.05. P-values will be presented with 3 decimals and p-values that are less than 0.001 will be presented as <0.001.

Continuous (non-survival-related) data will be summarized using descriptive statistics: number of observations (n), mean, standard deviation (SD), median, minimum, and maximum. Frequencies and percentages will be used to summarize categorical (discrete) data. Presentations of categorical data will generally suppress percentages for items where the count is zero in order to draw attention to the nonzero counts. In general, mean, standard deviation, median, minimum, maximum, and percentages will be presented with one decimal.

Unless otherwise stated, confidence intervals, when presented, will be constructed at the two-sided 95% level. For binomial variables, the 95% confidence intervals will be constructed using the normal approximation without continuity correction.

Data listings will present all data collected on case report forms (CRFs) by study drug, center, and patient number.

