11.1.3 LABORATORY ASSESSMENTS

Chemistry, hematology, urinalysis and coagulation profile will be assessed at baseline and over time. Summary statistics for these parameters will be presented by visit for the actual value and change from baseline for each test in each laboratory category (hematology, chemistry, urinalysis, and coagulation profile). Shift tables will be presented for shifts from baseline lab categories to end of study laboratory

category. The three laboratory categories will be: L (below lower bound of normal range), N (within normal range), and H (above higher bound of normal range).

If a lab value is reported using a non-numeric qualifier (e.g., less than (<) a certain value, or greater than (>) a certain value), the given numeric value will be used in the summary statistics, ignoring the non-numeric qualifier.

If a patient has repeated laboratory values for a given time point, the value from the first evaluation at that time point will be used for summarization purposes. For the purpose of determining baseline, the last non-missing observation on or prior to first dose of CAM2038.

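### Low/Normal/High laboratory shifts cannot show a rise in AST, ALT, bilirubin or creatinine in patients who enter above the upper limit of normal, and no planned table counts patients by threshold

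*SAP*

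**What the plan says.** **Shift tables.** SAP 11.1.3 states: "Shift tables will be presented for shifts from baseline lab categories to end of study laboratory" category. The categories are "L (below lower bound of normal range), N (within normal range), and H (above higher bound of normal range"). High has no grading above the upper bound.

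**Other laboratory outputs.** The same section adds: "Summary statistics for these parameters will be presented by visit for the actual value and change from baseline for each test". Under SAP 6.0 continuous data are described by "number of observations (n), mean, standard deviation (SD), median, minimum, and maximum". When a test is repeated at a time point, SAP 11.1.3 summarises the first evaluation. For chemistry, Appendix A lists summaries (Tables 14.3.13.1/.2), shifts (Tables 14.3.14.1/.2) and Listing 16.2.8.3. It lists no table of laboratory abnormalities by threshold.

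**Who may enter.** Protocol 7.5 excludes "Aspartate aminotransferase (AST) levels ≥ 3 X the upper limit of normal, alanine aminotransferase (ALT), levels ≥ 3 X the upper limit of normal", and total bilirubin or creatinine at or above 1.5 x ULN, on the Screening tests. Criterion 8 excludes "Hepatitis, unless under stable treatment, at the discretion of the Investigator".

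**What the protocol foresees.** Protocol 11.3.3: "Shift tables and tabular summaries of abnormalities will be provided, where appropriate".

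**Contrast.** For QT, QTcB and QTcF, SAP 11.1.6 counts patients in four absolute bands, at each visit and at any visit, and in three bands of increase.

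**The concern.** The shift table is the only categorical laboratory analysis in the SAP, and its top category has no ceiling. The entry criteria let patients start inside that category for exactly the tests used to judge hepatic and renal function at entry. For those patients the table can show improvement to Normal, but never deterioration. For patients normal at baseline it shows that the limit was crossed, but not how far.

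Laboratory tests are a listed safety variable (Protocol 9.6) under a primary objective of long-term safety. A reader of the study report would reasonably ask how many patients reached 3 x ULN for a transaminase, or 1.5 x ULN for bilirubin or creatinine, on treatment. These are the levels at which the protocol itself bars entry. No planned table answers that question.

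**Working it through.** The plan gives no figure to reproduce, so the check applies the SAP's category rule to pairs of values.

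**Inputs**
- Categories and time points: SAP 11.1.3 (L, N, H; baseline to end of study).
- Baseline range: Protocol 7.5, criterion 11. Protocol Table 3 schedules pre-dose laboratory tests at Screening only, so the baseline value is normally the Screening value.
- End-of-study values: illustrative, not from the documents.

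**Rule:** value > 1 x ULN gives H; value within the normal range gives N.

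| Baseline (x ULN) | End of study (x ULN) | Fold change | Cell in the shift table |
|---|---|---|---|
| 0.8 | 1.1 | 1.1/0.8 = 1.38 | N to H |
| 0.8 | 20 | 20/0.8 = 25 | N to H |
| 1.2 | 3 | 3/1.2 = 2.5 | H to H |
| 1.2 | 10 | 10/1.2 = 8.33 | H to H |
| 2.0 | 10 | 10/2.0 = 5 | H to H |
| 2.9 | 20 | 20/2.9 = 6.9 | H to H |
| 2.9 | 1.1 | 1.1/2.9 = 0.38 | H to H |

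Baselines of 2.0 and 2.9 are possible for AST and ALT. A baseline of 1.2 is possible for all four analytes. A five-fold rise and a fall of more than half share a cell, and a 1.38-fold rise shares a cell with a 25-fold rise.

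**Do the by-visit means show it?** One patient moving from b to e shifts the mean change by (e - b)/n. From 2 to 10 x ULN:
- n = 100: 8/100 = 0.08 x ULN
- n = 228: 8/228 = 0.035 x ULN

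The mean does not show it. The maximum does, but it describes one extreme value and not how many patients rose.

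**How many patients could be affected?** The documents give no share of patients above ULN at baseline. Under assumed shares of 10%, 25% and 50%, the number unable to register an upward shift would be 23, 57 and 114 of 228 enrolled, or 10, 25 and 50 of 100 with full exposure. The range of shares is an assumption, and these are not counts of patients who worsen. The 228 base is also too large for the shift table. Table 3 schedules one later laboratory test, at the end of treatment, and the planned dropout is about 50%, so about 228 x 0.5 = 114 patients would have that scheduled value unless dropouts are also tested.

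**The case against.** The strongest reply is that the report does not depend on the shift table. Protocol 9.4.1 counts an abnormal laboratory finding, or worsening of an existing abnormality, as an adverse event. Section 9.4.1.1 names worsening baseline conditions and clinically significant laboratory findings. Section 9.4.3 has the Investigator mark each flagged value as clinically significant or not. SAP 11.1.2 then counts patients with such events. In addition, the maximum change is reported and every chemistry value is listed. The study is uncontrolled, no laboratory hypothesis test is specified, and an entry limit is not an on-treatment threshold.

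Most of this stands, and it limits the point. What it does not supply is an objective count. The adverse event route rests on Investigator judgment. Protocol 9.4.3 allows a clinically significant value to be tied to medical history instead of an event, although 9.4.1.1 still calls for an event when a baseline condition worsens. Event severity is defined by treatment needed and interference with daily living, not by laboratory level.

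A reader might infer four stronger things, none of which the documents support:
- *Liver worsening would disappear from the report.* The maximum, the listing and the adverse event tables remain.
- *Every patient with stable hepatitis is High to High.* Such a patient with normal enzymes who worsens is Normal to High.
- *The SAP breaches the protocol.* The protocol's commitment to summaries of abnormalities is qualified by appropriateness, and SAP 11.1.2 leaves room for further safety analyses. This is thin specification, not a breach.
- *The patients concerned have the least hepatic reserve.* Nothing in the documents shows that a transaminase below 3 x ULN measures reserve, and criterion 13 lists severe hepatic insufficiency among its grounds for exclusion.

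**Conclusion.** The point holds as a weakness in how laboratory data are categorised. For AST, ALT, total bilirubin and creatinine, a patient above ULN at baseline cannot register an upward shift, and Normal to High carries no information on degree. This follows from SAP 11.1.3 and Protocol 7.5 without further assumption. No planned table counts patients crossing a liver or renal threshold, although the SAP does so for QT/QTc.

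Its size in patients cannot be derived, because the documents give neither the share above ULN at baseline nor a rate of worsening. Existing outputs would still reveal an extreme individual rise, so this is a worthwhile, inexpensive improvement and not a flaw that undermines the safety assessment.

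**What to change.** Revise SAP 11.1.3 and Tables 14.3.14.1/.2 before database lock, for AST, ALT, total bilirubin and creatinine:

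1. Add a shift in multiples of ULN by baseline band. For AST and ALT: <=1, >1 to <3, and >=3 x ULN, plus one prespecified higher band. For bilirubin and creatinine: <=1, >1 to <1.5, and >=1.5 x ULN. The documents give no value for the higher band, so the sponsor must choose and state it. State that these are reporting bands only, not rules for managing patients.
2. Add the number and percent of patients in each band by worst post-baseline value, including unscheduled and repeat tests. State that this table is exempt from the first-evaluation rule, and use the number of patients with any post-baseline test as denominator.
3. Keep L/N/H for the other analytes.

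With these bands, 2 to 10 x ULN appears as a rise, and 0.8 to 1.1 is separated from 0.8 to 20. Movement within a band, such as 2.9 to 1.1, still shows as no change, so the change-from-baseline summaries remain necessary.

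The cost is SAP wording and one or two table panels, with no new samples. With only one scheduled post-baseline test, much of what the worst-value table adds will come from unscheduled tests, which are taken selectively. A footnote should say so.

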11.1.4 VITAL SIGNS

Vital signs will be assessed over time. Vital sign values and change from baseline in the vital signs will be summarized.

11.1.5 PHYSICAL EXAMINATION

Physical examination data at Screening will be summarized.

11.1.6 12-LEAD ELECTROCARDIOGRAM

12-Lead ECGs will be assessed over time. The ECG variables will include ventricular heart rate and the PR, QRS, QT, QTcB and QTcF intervals. The ECGs will be signed and dated by a medically-qualified individual to confirm review of the ECG and verify whether any abnormalities are clinically significant.

Number and percent of patients in each ECG finding category (normal, abnormal not clinically significant, and abnormal and clinically significant), will be summarized for each visit. Summary statistics will be presented for the actual value and change for each ECG parameter.

The number and percent of patients with QT, QTcB and QTcF intervals < 450 msec, 450 to <480, 480 to <500 and greater than/equal to 500 msec at each visit and overall (at any visit) will be summarized. Additionally, the number and percentage of patients with increases in these parameters of <30 msec, 30 to <60 msec and greater than/equal to 60 msec will be summarized at each visit.

11.1.7 INJECTION SITE EXAMINATION

The injection site will be visually inspected for evidence of erythema, edema, itching, pain, infection, bleeding, abnormal healing and any other abnormalities.

AEs that are believed to be associated with injection procedures will be summarized similarly to the summaries for other AEs (not associated with injection procedures).

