Diagnosis and Main Criteria for Inclusion: This study will enroll adult outpatients with opioid use disorder as defined by the Diagnostic and Statistical Manual of Mental Disorders – Fifth Edition (DSM-V). Subjects must meet one of the following criteria for BPN treatment history: 
Voluntarily seeking treatment for opioid use disorder (not currently on BPN treatment for at least last 60 days but seeking BPN treatment), or;Currently on SL BPN treatment
Investigational Product, Dosage and Mode of Administration: CAM2038 q1w: buprenorphine FluidCrystal [®] subcutaneous (SC) injection depot for once weekly administration (50 mg/mL) at doses of 8, 16, 24 and 32 mg (buprenorphine base) (0.16, 0.32, 0.48 or 0.64 mL SC injection). CAM2038 q4w: buprenorphine FluidCrystal [®] SC injection depot for once monthly administration (356 mg/mL) at doses of 64, 96, 128 or 160 mg (buprenorphine base) (0.18, 0.27, 0.36 or 0.45 mL SC injection).
Reference Therapy, Dosage and Mode of Administration: This is an open-label study, no reference therapy (placebo or active comparator) will be administered.
Duration of Study: This is a 12-month (48-week) treatment study. Subject with no previous exposure to CAM2038 will receive treatment for up 48 weeks.

Name of Sponsor/Company: Braeburn Pharmaceuticals
Name of Investigational Products: CAM2038 q1w (buprenorphine FluidCrystal® once-weekly injection depot) CAM2038 q4w (buprenorphine FluidCrystal® once-monthly injection depot)
Name of Active Ingredient: Buprenorphine
Criteria for Evaluation: Safety Endpoints: 
▪ Adverse events (AEs) and serious adverse events (SAEs)▪ Clinical laboratory tests▪ Electrocardiogram (ECG)▪ Vital signs▪ Physical and injection site examinations▪ Concomitant medications Efficacy Measures: 
▪ Urine toxicology results for illicit opioids▪ Self-reported illicit opioid use▪ Retention (%) in treatment▪ Work Productivity and Activity Impairment Questionnaire-General Health (WPAI-GH)▪ EQ-5D-5L Health Questionnaire▪ Patient Satisfaction Scale▪ Measures of opioid withdrawal:
○ Clinical Opiate Withdrawal Scale (COWS)○ Subjective Opiate Withdrawal Scale (SOWS)▪ Measures of opioid craving:
○ Desire to Use visual analogue scale (VAS)○ Need to Use VAS▪ Urine toxicology results for other drugs of abuse

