9.4.8. Injection Site Examination

CAM2038 injection sites will be examined during each scheduled visit for any signs of adverse site reactions, including erythema, pruritus, edema, pain, etc. If needed, a photograph of the adverse site reactions will be taken and shared with the medical monitor for review. The pain scale will be completed by the subjects within 10 minutes after each injection. The new injection site will also be examined within 15 minutes after each injection to determine if any site related AEs have occurred. Injection site evaluation forms will be included in the Trial MOP. Subjects will also be queried specifically about local tolerability AEs in connection to the examinations.

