| TABLE 14.3.16.2 | Shift from Baseline in Laboratory Tests: Coagulation Profile (Full Exposure Safety Population) |
| TABLE 14.3.17.1 | Summary of Vital Signs over Time (Overall Safety Population) |
| TABLE 14.3.17.2 | Summary of Vital Signs over Time (Full Exposure Safety Population) |
| TABLE 14.3.18.1 | Summary of 12-Lead ECG Results (Overall Safety Population) |
| TABLE 14.3.18.2 | Summary of 12-Lead ECG Results (Full Exposure Safety Population) |
| TABLE 14.3.19.1 | Summary of 12-Lead ECG Individual Parameters (Overall Safety Population) |
| TABLE 14.3.19.2 | Summary of 12-Lead ECG Individual Parameters (Full Exposure Safety Population) |

List of Listings

| Number | Title |
|------------------|-------------------------------------|
| LISTING 16.2.1.1 | Patient Meeting Inclusion Criteria |
| LISTING 16.2.1.2 | Patients Meeting Exclusion Criteria |
| LISTING 16.2.2 | Protocol Deviations |

| | |
|------------------|--|
| LISTING 16.2.3 | Patient Disposition |
| LISTING 16.2.4.1 | Demographics |
| LISTING 16.2.4.2 | Psychosocial History |
| LISTING 16.2.4.3 | Medical History |
| LISTING 16.2.4.4 | Substance Abuse History and Treatment |
| LISTING 16.2.5.1 | CAM2038 Injection |
| LISTING 16.2.5.2 | Injection Site Examination/ Treatment Compliance |
| LISTING 16.2.6.1 | COWS, SOWS |
| LISTING 16.2.6.2 | Need to Use and Desire to Use VAS |
| LISTING 16.2.6.3 | Urine Toxicology Results for Illicit Opioids |
| LISTING 16.2.6.4 | Self-Reported Illicit Opioid Use |
| LISTING 16.2.6.5 | Urine Toxicology Results for Other Drugs of Abuse |
| LISTING 16.2.6.6 | Work Productivity and Activity Impairment Questionnaire General Health (WPAI-GH) |
| LISTING 16.2.6.7 | EQ-5D-5L Health Questionnaire |
| LISTING 16.2.6.8 | Patient Satisfaction Scale |
| LISTING 16.2.6.9 | Psychosocial Counseling |
| LISTING 16.2.7.1 | Adverse Events |
| LISTING 16.2.7.2 | Serious Adverse Events |
| LISTING 16.2.7.3 | Adverse Events That Lead to Discontinuation from Treatment/Study |
| LISTING 16.2.7.4 | Adverse Events That Have Death as the Outcome |
| LISTING 16.2.7.5 | Death Reports |
| LISTING 16.2.7.6 | Prior and Concomitant Medications/Procedures |
| LISTING 16.2.8.1 | Lab Test Samples |
| LISTING 16.2.8.2 | Clinical Hematology |
| LISTING 16.2.8.3 | Clinical Chemistry |
| LISTING 16.2.8.4 | Clinical Coagulation Profile |
| LISTING 16.2.8.5 | Urinalysis |
| LISTING 16.2.8.6 | Serology |
| LISTING 16.2.8.7 | Pregnancy Test |
| LISTING 16.2.8.8 | Pregnancies |

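### The SAP plans no summary of injection site examination findings, to which the protocol commits, and does not say how the post-injection pain scale will be reported

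*SAP*

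**What the plan says.** The protocol synopsis lists "Physical and injection site examinations" among the safety endpoints, on a separate line from AEs, and section 9.6 repeats the item as a safety variable. Protocol section 11.3.3 states: "Data for clinical laboratory tests, ECG, vital signs, and physical and injection site examinations will be summarized using standard descriptive and change from baseline statistics". It then adds: "Shift tables and tabular summaries of abnormalities will be provided, where appropriate". Section 11.2 requires safety results for both the Overall and the Full Exposure Safety Population.

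On data collection, protocol section 9.4.8 has sites examined at each scheduled visit and the new site examined within 15 minutes of injection. It also says: "The pain scale will be completed by the subjects within 10 minutes after each injection". In the same section: "Subjects will also be queried specifically about local tolerability AEs in connection to the examinations".

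SAP section 11.1.7 has two paragraphs. The first describes the procedure: "The injection site will be visually inspected for evidence of erythema, edema, itching, pain, infection, bleeding, abnormal healing and any other abnormalities". The second says that AEs thought to be associated with the injection will be summarised in the same way as other AEs. Appendix A contains Listing 16.2.5.2, "Injection Site Examination/ Treatment Compliance", and no table of examination findings.

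**The concern.** The primary objective is safety and tolerability. Protocol section 5.4 describes local injection-site reactions, including ulcers and necrotic wounds, as the most severe side-effects specific to the product. The two depots also differ: protocol section 8.2 gives 50 mg/mL in an ethanol-containing vehicle for q1w and 356 mg/mL with N-methyl-2-pyrrolidone for q4w.

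If the SAP is followed as written, an endpoint that the protocol lists separately from AEs is never summarised in its own right. A sign or pain rating that is not also reported as an AE would reach the study report at most in a listing. The AE tables cannot fully stand in for the missing summary. They count a patient once per preferred term. They add total event counts but no rate per injection, and neither SAP section 11.1.2 nor any injection-related table title mentions q1w or q4w. How often local findings recur over repeated injections, and whether this differs by product, is a natural question for a 48-week depot study, and no planned table addresses it.

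**Working it through.** The plan gives no figure to reproduce here. The check is a cross-reading of the two documents, a count of planned outputs and a rough measure of data volume.

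**1. Commitment against plan**

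| Item | Protocol | SAP |
|---|---|---|
| Examination findings | Endpoint (synopsis, 9.6); descriptive summary (11.3.3) | Procedure described (11.1.7); no summary method |
| Populations | Both (11.2, 11.3.3) | Both, for safety analyses in general (11.0) |
| Pain scale | After each injection (9.4.8) | Not mentioned; pain appears only as an inspection item (11.1.7) |
| Record of a change | SAP to contain amendments to proposed analyses (11.1) | History (1.0) names only sample size and the new-to-treatment analysis |

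In protocol section 11.3.3 the qualifier about appropriateness belongs to the sentence on shift and abnormality tables, not to the sentence that promises descriptive summaries. The neighbouring SAP sections on vital signs, physical examination, ECG and the suicide scale each state a summary of their own data. Section 11.1.7 does not.

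**2. Count of Appendix A outputs**

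- Injection-related AE tables: 14.3.2.3 to 14.3.2.6 = 4. Items .3 and .4 in each of the seven groups 14.3.3 to 14.3.9 (in group 14.3.5 these are 14.3.5.3 and 14.3.5.4) = 7 × 2 = 14. Total 4 + 14 = 18, or 9 per safety population.
- Tables of examination findings: 0.
- Outputs naming the pain scale: 0.
- Listings of the examination: 1 (16.2.5.2).

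**3. Product split.** SAP section 11.1.1 gives patients, injections and exposure years by dose and by product. SAP section 6.0 sorts listings by study drug. No product split is stated for AEs or for local findings.

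**4. Volume (illustrative).** Assume one product throughout, all scheduled injections given and no boosters.

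- q4w at Weeks 1, 5, …, 45: (45 − 1)/4 + 1 = 12 injections.
- q1w over 48 weeks: 48 injections.
- Minimum of 100 fully exposed patients: 100 × 12 = 1,200 to 100 × 48 = 4,800 pain ratings.
- Planned enrolment with 50% dropout: 228 × 0.5 = 114 patients, giving 114 × 12 = 1,368 to 114 × 48 = 5,472.

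Injections in patients who drop out would add to these counts, as would boosters. Switching between products would move the total within the range.

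**5. Can the protocol's wording be met literally?** Not fully. Protocol section 8.1 rotates sites: a q1w site is not reused for at least 8 weeks, and a q4w site is not reused during the study. Table 3 schedules no site examination at Screening. A freshly chosen site therefore has no pre-injection measurement, so change from baseline has no clear meaning. Frequencies do.

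**The case against.** The strongest reply is that local tolerability is well covered by AEs. This largely stands. The 18 tables include severity, time to onset and duration, relationship, serious events and discontinuations. Protocol section 9.4.1 defines an AE to include any unfavourable and unintended sign, and section 9.4.1.1 requires recording whatever the severity or causality. Section 9.4.8 uses the post-injection examination to detect AEs and has patients asked about them. Many mild local signs should therefore become AEs. A reader might infer that local tolerability is left largely unanalysed; the documents do not support that. What remains is that the protocol lists the examination separately from AEs and promises its own summary, and that conversion to an AE still involves judgement.

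A reader might also infer that the SAP abandoned the endpoint. It did not. SAP section 11.0 says safety evaluation will draw on clinically significant changes in injection site examinations, and section 11.1.2 allows other safety analyses as appropriate. Neither names a statistic or an output, so the gap stays open.

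The pain-scale part is weaker than the examination part. The scale is not itself a listed safety variable, has no row in Table 3, and its type and range are not given. The forms are in the Manual of Procedures, which is not available here. SAP section 6.0 would list the ratings if they are on a CRF.

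Finally, this is an open-label, single-arm, descriptive study, and no test or decision rule depends on these tables. The data are collected in any case, so summaries could be added later. That limits the harm, but tables chosen after the data have been seen carry less weight than tables specified beforehand.

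**Conclusion.** The point holds as a protocol-to-SAP gap. The SAP omits the descriptive summaries of injection site examination findings to which the protocol commits, does not say how pain ratings will be reported, and does not record the departure. Local tolerability is analysed only through investigator-reported AEs, with no stated split by product.

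The size is 0 planned tables of findings and 0 outputs naming the pain scale, against 18 injection-related AE tables and 1 listing. The 1,200 to 4,800 pain ratings show how much data has no planned summary. They say nothing about how many reactions AE reporting would miss, which the documents do not allow one to estimate. The examination part rests on the documents alone. The pain part also assumes that the ratings are captured in a form that can be tabulated. The change should be made because the data serve the primary objective and the cost is small.

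**What to change.** In SAP section 11.1.7 and Appendix A, add for both safety populations:

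- The number and percent of patients with each examination finding, by visit and by product at the most recent injection (q1w, q4w). State how boosters are handled: they are q1w injections even in a patient maintained on q4w.
- In a separate display, the percent of injections followed by each finding, by product. Patient and injection denominators should not be mixed. Patients on q1w have up to 48/12 = 4 times as many scheduled injections as those on q4w, so the percent of patients ever affected is not comparable between products by itself. SAP section 11.1.1 already plans the injection counts. Injections within a patient are correlated, so the simple binomial interval in SAP section 6.0 should not be attached to these percentages.
- A by-product summary of the pain ratings, in a form suited to the scale on the CRF: category frequencies if ordinal, descriptive statistics if numeric.

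State that frequency summaries replace change from baseline for this endpoint, because rotated sites have no pre-injection baseline, and record that as a change from protocol section 11.3.3. If the sponsor prefers to rely on AEs alone, the SAP should say so and justify it.

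The cost is two or three extra descriptive tables per population, with no new data collection.
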